5.5.2. Withdrawal Procedures

In the event that the decision is made to permanently discontinue the study drug, the subject will be withdrawn from the study and the end-of-treatment (EOT) visit should be conducted. Reasonable efforts should be made to have the subject return for a follow-up visit. These visits are described in [Section 6](#). The last date of the last dose of study drug and the reason for subject withdrawal will be recorded in the electronic case report form (eCRF).

If a subject is withdrawn from the study:

[figure not shown]
- The study monitor or sponsor must be notified.
- The reason(s) for withdrawal must be documented in the subject's medical record and in the eCRF.
- The EOT visit should be performed.

[figure not shown]
- The date of the EOT visit should be recorded in the IRT.
- Subjects must be followed for safety until the time of the follow-up visit or until study drug-related toxicities resolve, return to baseline, or are deemed irreversible, whichever is longest.

If the subject discontinues study treatment and actively withdraws consent for collection of follow-up data (safety follow-up or disease assessment), then no additional data collection should occur; however, subjects will have the option of discontinuing study drug but continuing in the follow-up period of the study for safety/efficacy assessments.

5.6. Concomitant Medications

All concomitant medications and treatments must be recorded in the eCRF and ideally should remain stable through the end of the treatment portion of the study. All prior medications for AD and any medications received up to 30 days before randomization will be recorded in the eCRF. Concomitant treatments and/or procedures that are required to manage a subject's medical condition during the study will also be recorded in the eCRF.

6. STUDY ASSESSMENTS

All study assessments will be performed as indicated in the schedule of assessments ([Table 2](#)), and all laboratory assessments will be performed as indicated in [Table 3](#).

Table 2: Schedule of Assessments

Evaluation	Protocol Section	Screening		Treatment					EOT	Follow-Up 30 ± 7 Days After Last Dose
		Day -28 to -1	Baseline Day 1	Week 2 Day 14 ± 3 Days	Week 4 Day 28 ± 3 Days	Week 8 Day 56 ± 7 Days	Week 10 Day 70 ± 3 Days	Week 12 Day 84 ± 7 Days		
Administrative procedures										
Informed consent	7.1	X								
Contact IRT	7.2	X	X	X	X	X	X	X	X	X
Inclusion/exclusion criteria	3	X	X							
Demography and medical history	7.3	X								
Prior/concomitant medications	7.4	X	X	X	X	X	X	X	X	X
Dispense study drug and diary card	7.10.1		X	X	X	X	X			
Apply study drug	5.2		X	X	X	X	X			
Collect study drug tubes and review diary cards	7.10.1			X	X	X	X	X	X	
Assess compliance	5.3			X	X	X	X	X	X	
Safety procedures/assessments										
Comprehensive physical examination (height and weight at screening only)	7.5.2.1	X								X
Targeted physical examination	7.5.2.2		X	X	X	X	X	X	X	X
Vital signs	7.5.3	X	X	X	X	X	X	X	X	X
Hematology and chemistry assessments	7.5.5	X	X	X	X	X	X	X	X	
Free T4 and thyroid stimulating hormone		X								
Urinalysis	7.5.5.3	X								
Pregnancy test ^a	7.5.5.4	X	X	X	X	X	X	X	X	X
Serology	7.5.5.5	X								
12-lead ECG	7.5.4	X								
Assess AEs	7.5.1	X	X	X	X	X	X	X	X	X
Efficacy assessments										
EASI scoring	7.6.1	X	X	X	X	X	X	X	X	X
BSA treated w/study drug (4 regions and overall)	7.6.5	X	X	X	X	X	X	X	X	X
IGA	7.6.2	X	X	X	X	X	X	X	X	X
Photography	7.6.6		X		X					
Itch Numerical Rating Scale	7.6.4	Diary is completed each evening from screening through the last dose of study drug.								

^a All women will have a serum pregnancy test conducted at the screening visit and urine pregnancy tests conducted at all other visits (including baseline).

Table 3: Clinical Laboratory Assessments

Serum Chemistries	Hematology
Albumin	Hematocrit
Alkaline phosphatase	Hemoglobin
ALT	Mean corpuscular volume
AST	Platelet count
Bicarbonate	Red blood cell count
Blood urea nitrogen	Reticulocyte count
Calcium	White blood cell count
Chloride	White blood cell differential (5 part):
Creatinine	
 • Basophils • Eosinophils • Lymphocytes • Monocytes • Neutrophils
Glucose	
Lactate dehydrogenase	
Phosphorus	
Potassium	
Sodium	
Total bilirubin	
Total serum protein	
Other	Serology
Urinalysis	Hepatitis B surface antigen
Urine pregnancy test (at site)	Hepatitis B core antibody
Serum pregnancy test	Hepatitis B core IgM antibody
Free T4	Hepatitis C virus antibody
TSH	HCV-RNA (only performed if antibody positive)
	HIV antibody

HCV-RNA = hepatitis C virus ribonucleic acid; IgM = immunoglobulin M; TSH = thyroid-stimulating hormone.

6.1. Screening

Screening is the interval between the signing of the ICF and the day that the subject is enrolled in the study. Informed consent must be obtained before performing any study-specific procedures. Assessments that are required to demonstrate eligibility may be performed over the course of 1 or more days during screening.

Results from the screening evaluations will be reviewed to confirm subject eligibility before randomization or the administration of study drug. Tests with results that fail eligibility requirements may be repeated once during screening if the investigator believes the results to be in error. Additionally, a subject who fails screening may repeat the screening process 1 time if the investigator believes that there has been a change in eligibility status (eg, following recovery from an infection).

6.2. Baseline

The results from the screening evaluations will be reviewed to determine whether the subject continues to meet the eligibility requirements as specified in the Protocol.

Subjects who have signed the ICF and meet all the entry criteria (see [Section 3](#)) may be enrolled or randomized in the study on Day 1.

6.3. Treatment

Subjects who meet all of the study inclusion criteria and none of the exclusion criteria will return to the study site on Day 1 of administration. Dates for subsequent study visits will be determined based on this day and should occur within the visit windows outlined in the schedule of assessments ([Table 2](#)).

The treatment period begins when the subject receives their first dose of study drug, which will be administered in the clinic. The amount of study medication to be obtained from the pharmacy is determined by the BSA to be treated. On Day 1, the prescribed dose is to be determined by weighing a tube before and after the subject applies a thin film of study drug to the affected areas. For each 1% of BSA (palm with fingers) to be treated with study drug, approximately 2 inches (5 cm) of study drug may be used. Subjects will be advised to limit use to no more than 1 tube per application. Tubes of INCB018424 cream, triamcinolone 0.1% cream, or vehicle cream will be dispensed to subjects with detailed application instructions. The face and intertriginous areas may be treated with hydrocortisone 2.5% cream throughout the study.

For all study visits, subjects should apply the morning dose of study drug in the clinic to assess understanding of dispensing and application. A designated site staff member will be assigned to dispense and collect study drug, as well as instruct and assist with application of study drug during the clinic visits. This person should not have study responsibilities that involve either efficacy or safety assessments. Returned study drug should be collected before other study assessments being performed. Study drug should be dispensed at the end of the visit by the same designated staff, after other visit assessments have been completed. The subject should be counseled at this time regarding questions about dose or method of application.

Subjects who are noncompliant with study drug (defined as < 80% or > 120% compliant based on tube weight) will have the administration instructions reinforced by the investigator or a qualified designee. After reinforcement, subjects who again fail to meet < 80% or > 120% compliance benchmarks in a subsequent visit will be considered for withdrawal from the study. In such cases, the sponsor should be consulted by the investigator for instruction on the proper handling of the subject before withdrawal.

6.4. End of Treatment/Early Termination

If a decision is made that the subject will permanently discontinue study drug, then the EOT visit should be conducted. If the EOT visit coincides with a regular study visit, then the EOT evaluations will supersede those of that scheduled visit, and the data should be entered in the EOT page in the eCRF. If this decision does not coincide with a regular visit, reasonable efforts should be made to have the subject return to the site to have the EOT procedures completed.

6.5. Follow-Up

After the EOT visit (Weeks 8 or 12, or early termination), subjects will have follow-up assessments 1 month later to monitor for durability of effect (relapse rate), AEs, medication history, vital signs, and clinical assessments. If prohibited treatment for AD is started, an earlier follow-up visit may be performed. A final and thus end-of-study visit should be performed ideally no earlier than 30 days after the last dose of study drug. Adverse events and SAEs must be reported up until at least 30 days after the last dose of study drug, the date of the follow-up visit, or until toxicities resolve, return to baseline, or are deemed irreversible, whichever is longer. If needed, a follow-up phone call will be conducted to determine any AEs or SAEs during the 30 days after the last dose of study drug. Reasonable efforts should be made to have the subject return for the follow-up visit and report any AEs that may occur during follow-up.

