4. INVESTIGATIONAL PLAN

4.1. Overall Study Design

This is a randomized, vehicle- and active (triamcinolone 0.1% cream)-controlled study in subjects with mild to moderate AD. The study is double-blinded for vehicle, INCB018424 doses, and active control. Approximately 300 subjects will be randomized 1:1:1:1:1:1 to INCB018424 1.5% BID, INCB018424 1.5% QD, INCB018424 0.5% QD, INCB018424 0.15% QD, vehicle BID, and active control (triamcinolone 0.1% cream BID) and stratified by EASI score (≤ 7 and > 7). Subjects receiving QD regimens will apply vehicle at the evening application. Subjects will receive blinded study drug for 8 weeks. Subjects randomized to QD regimens will apply vehicle for the evening application. Subjects randomized to triamcinolone will apply triamcinolone 0.1% cream BID for 4 weeks and vehicle cream for 4 weeks to not exceed the allowable triamcinolone application duration ([Figure 2](#)).

At Week 8, subjects who meet criteria (compliant with the Protocol and no safety concerns) will be offered open-label treatment with INCB018424 1.5% cream BID for 4 weeks.

Through Week 8, subjects should continue to treat areas identified for treatment at baseline even if the area begins to improve. After Week 8, areas which were treated before Week 8 that are no longer symptomatic are not required to be treated.

Subjects will have follow-up assessments 1 month after the last application of study drug.

Study drug (INCB018424 cream, vehicle, or triamcinolone) may not be applied to the face or intertriginous areas. The face and intertriginous areas may be treated with hydrocortisone 2.5% cream during the study. Assessments of BSA should be based on treated areas (excluding the face and intertriginous areas that cannot be treated with study drug).

Subjects who develop additional areas of AD after the initiation of treatment may treat these additional areas (except the face and intertriginous areas) as long as the total treated BSA does not exceed 20% and there are no safety concerns regarding the additional application of study drug.

Subjects may continue to use bland emollients that do not contain urea or ceramides during the study. If bland emollients are used, the type of cream and amount of application should remain consistent for the duration of the study.

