4. DATA HANDLING DEFINITIONS AND CONVENTIONS

4.1. Scheduled Study Evaluations and Study Periods

4.1.1. Definitions for Day 1, Baseline, and the Last Available Value

Day 1, baseline, and last available value for the DB period and the open-label period are defined in [Table 1](#).

Table 1: Definition of Day 1, Baseline, and Last Available Value

Study Period	Treatment Group	Day 1	Baseline	Last Available Value
DB period	INCB018424 cream 1.5% BID 1.5% QD 0.5% QD 0.15% QD Vehicle triamcinolone	Date of first application or date of randomization for subjects randomized but not treated in the DB period	The last nonmissing measurement obtained on or before the day of the first dose.	The last nonmissing measurement obtained after the first dose, and within 30 days after the last dose in the DB period or before the first dose in the extension period, whichever is earlier.
Open-label period	INCB018424 cream 1.5% BID	Date of first application in DB period	The last nonmissing measurement obtained on or before the day of the first dose in DB period	The last nonmissing measurement obtained after the first dose and within 30 days after the last dose.
	INCB018424 cream 1.5% QD 0.5% QD 0.15% QD Vehicle triamcinolone	Date of first application in open-label period	The last nonmissing measurement obtained on or before the day of the first dose in the open-label period	The last nonmissing measurement obtained after the first dose in open-label period and within 30 days after the last dose.

When scheduled assessments and unscheduled assessments occur on the same day and time of the assessment or when the first dose is not available, use the following convention to determine the baseline value:

- If both a scheduled and an unscheduled visit are available on the day of the first dose and the time is missing, use the scheduled assessment as baseline.
- If all scheduled assessments are missing on the day of the first dose and an unscheduled assessment is available, use the unscheduled assessment as baseline.

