5.2. Treatment Groups

This is a study in subjects with AD, with a DB, randomized, and vehicle- and active (triamcinolone 0.1% cream)-controlled treatment period followed by an optional open-label treatment period. Data will be summarized based on the treatment regimen that was initially assigned or that subjects received during the DB period.

- DB period versus open-label period:
 - INCB018424 1.5% BID
 - INCB018424 1.5% QD
 - INCB018424 0.5% QD
 - INCB018424 0.15% QD
 - TAC*
 - Vehicle BID

*Active control (triamcinolone 0.1% cream) BID for 4 weeks followed by vehicle cream BID for 4 weeks.

Table summaries, unless otherwise indicated, will present data by treatment group. The results will be summarized and presented separately for the DB period and open-label period.

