7. EFFICACY

7.1. General Considerations

For continuous measurements, summary statistics will include sample size, mean, median, standard deviation, standard error of the mean, minimum, and maximum. For all continuous variables, both the actual value and change and/or percentage from baseline (if available) will be analyzed.

For categorical measurements, summary statistics will include sample size, frequency, and percentages.

All by-visit analyses will include the follow-up period if the data are available.

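### The follow-up visit is meant to show durability, but the SAP's by-visit rule gives a selected double-blind column and an open-label column that all follows 1.5% BID

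*Protocol*

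**What the plan says.** Protocol section 6.5 states the purpose of the visit: "subjects will have follow-up assessments 1 month later to monitor for durability of effect (relapse rate", alongside AEs, vital signs and other checks. The same sentence lists the routes into it: "After the EOT visit (Weeks 8 or 12, or early termination". The schedule (Protocol Table 2) places the visit 30 ± 7 days after the last dose and includes EASI and IGA. The itch diary stops with treatment, so it gives no follow-up value.

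Open-label entry at Week 8 is not randomized. Under Protocol section 4.1, "subjects who meet criteria (compliant with the Protocol and no safety concerns) will be offered open-label treatment". It is optional (Protocol section 4.4), and every entrant uses 1.5% BID.

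On analysis, SAP section 7.1 says: "All by-visit analyses will include the follow-up period if the data are available". SAP section 5.2 sets the grouping: "Data will be summarized based on the treatment regimen that was initially assigned or that subjects received during the DB period". It then adds: "The results will be summarized and presented separately for the DB period and open-label period". SAP Table 1 ends the double-blind last available value within 30 days of the last double-blind dose or "before the first dose in the extension period, whichever is earlier". For the open-label period, the same table gives the 1.5% BID group its double-blind baseline and every other group a new baseline at open-label entry.

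In SAP Appendix A, the double-blind tables by visit for EASI, EASI response, IGA responders and Itch NRS are titled as ending at Week 8. ITT Table 2.1.3.5 (IGA improvement by visit) and the ITT by-visit figures carry no such limit.

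**The concern.** A by-visit display invites the reader to run an eye from Week 8 to follow-up and take the change as what happens off drug. That needs the same subjects in both columns, coming off the treatment named in the row. The SAP 7.1 rule secures neither. Who appears at follow-up in the double-blind display depends on who declined, was not eligible for, or stopped before the open-label period. What the open-label subjects had just come off is 1.5% BID, whatever the row label says.

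At stake is the one purpose that the protocol gives this visit beyond safety. An apparent relapse, an apparent lasting benefit, or a difference between arms could come from the composition of the column or from the open-label treatment. It need not come from the durability of the randomized regimen.

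**Working it through.** The documents give no relapse rate, open-label uptake or follow-up figure, so there is nothing to reproduce. The check traces where each follow-up value goes and then shows how much the routes could matter. Assumed figures are marked.

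**Step 1. Where each value goes when the periods are kept separate.**

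| Route to follow-up | Last treatment | Display | Baseline (SAP Table 1) |
|---|---|---|---|
| EOT at Week 8, no open label | Randomized regimen; vehicle in the triamcinolone arm | Double-blind | Double-blind |
| Early termination in the double-blind period | Whatever was in use at the time | Double-blind | Double-blind |
| EOT at Week 12, randomized to 1.5% BID | 1.5% BID | Open-label | Double-blind |
| EOT at Week 12, any other arm | 1.5% BID | Open-label | Open-label entry |

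The display column is inferred from SAP section 5.2; no visible text assigns follow-up visits to a period.

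**Step 2. Subjects per arm coming straight from Week 8.** Inputs: about 50 per arm (SAP section 3); uptake u assumed at 50% to 90%; no early dropout. Formula: 50 × (1 − u).

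| Assumed uptake | From Week 8 | After open-label 1.5% BID | Exact 95% CI if 40% relapse is observed (assumed) |
|---|---|---|---|
| 50% | 25 | 25 | 10/25: 21% to 61% |
| 70% | 15 | 35 | 6/15: 16% to 68% |
| 80% | 10 | 40 | 4/10: 12% to 74% |
| 90% | 5 | 45 | 2/5: 5% to 85% |

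The intervals are Clopper-Pearson: lower limit the 2.5% quantile of Beta(x, n − x + 1), upper limit the 97.5% quantile of Beta(x + 1, n − x). They treat everyone from Week 8 as an EOT responder, so a real denominator would be smaller. With 10% early dropout (assumed) and 80% uptake, 50 × 0.9 × 0.2 = 9 come from Week 8 and 5 from early termination.

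**Step 3. Selection alone can move the column, in either direction.** Assume that nobody changes after Week 8, that one arm has 80% responders at Week 8 and another 40%, and that entry depends on response. With r the Week 8 responder share, p the entry rate in responders and q in non-responders, the share at follow-up is r(1 − p) / [r(1 − p) + (1 − r)(1 − q)], and the number is 50 times the denominator.

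| p / q (assumed) | Arm at 80% | Arm at 40% | Gap between arms (40 points at Week 8) |
|---|---|---|---|
| 90% / 90% | 80% (n = 5) | 40% (n = 5) | 40 |
| 70% / 90% | 92% (n = 13) | 67% (n = 9) | 26 |
| 50% / 90% | 95% (n = 21) | 77% (n = 13) | 18 |
| 90% / 50% | 44% (n = 9) | 12% (n = 17) | 33 |

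Example, third row: 0.8 × 0.5 = 0.40 and 0.2 × 0.1 = 0.02, so 0.40/0.42 = 95% and n = 50 × 0.42 = 21. The apparent off-drug change runs from a gain of 37 points (40% to 77%) to a loss of 36 (80% to 44%), though no subject changed.

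**Step 4. The open-label baseline differs by arm.** Take two subjects who are both 75% below their double-blind baseline at follow-up, that is, at 25 when baseline is 100. One was randomized to 1.5% BID and shows 75%. The other was randomized to 1.5% QD and entered open label 65% improved, at 35; this subject shows 100 × (35 − 25)/35 = 28.6%. The 65% and 75% are the Week 4 planning means in Protocol Table 5, borrowed for illustration.

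**Step 5. Timing.** Triamcinolone subjects use vehicle in Weeks 4 to 8, so their Week 8-route follow-up falls about 4 + 4 = 8 weeks after active treatment. Starting a prohibited AD treatment can bring the visit forward (Protocol section 6.5), so timing can depend on outcome. The window runs to 30 + 7 = 37 days, past the 30-day limit on the last available value.

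**The case against.** The strongest reply is that the SAP does keep the periods apart. SAP section 5.2 says so, Table 1 stops the double-blind last available value before open-label dosing, there is a separate open-label population with its own tables, and most double-blind by-visit tables stop at Week 8. A reader might infer from SAP 7.1 and the grouping sentence that values taken after open-label 1.5% BID are pooled into the double-blind columns, so that a vehicle arm would seem to keep improving off drug. The documents do not support that reading. Table 1 defines a last available value, not a by-visit rule, but it points the same way as the rest. No size for pooled crossover should be quoted.

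It is also true that no listed endpoint and no visible table claims a relapse rate. Part of the SAP's secondary-analysis section is redacted, so the absence of a relapse definition cannot be held against the plan. And the open-label follow-up is not worthless: it describes the course after stopping 1.5% BID, and the arm randomized to 1.5% BID does not change regimen.

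What remains is the visible rule in SAP 7.1. It covers Table 2.1.3.5 and the ITT by-visit figures, which have no Week 8 limit, and it contradicts the titles of the tables that do. Keeping the periods separate removes pooling. It leaves the double-blind follow-up column selected and the open-label column labelled by an arm whose regimen, outside 1.5% BID, was not the last one used.

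**Conclusion.** The point holds in this limited form. Followed as written, SAP 7.1 produces follow-up columns that cannot show the durability of the randomized regimens. An apparent change off drug, or a difference between arms, can reflect selection or open-label 1.5% BID; it need not, and the direction cannot be known in advance. It would go too far to say that any relapse seen must be an artefact, or that the plan reports a misleading relapse rate.

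The size depends on uptake, which the documents do not give. At 50% to 90%, about 25 down to 5 of 50 subjects per arm reach follow-up directly from Week 8. The responder shares, entry rates and 40% relapse rate used above are also assumptions.

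The Week 4 primary and key secondary tests are unaffected. So are the other listed efficacy endpoints, which are tied to Weeks 2, 4 and 8 or are not by-visit summaries. This is worth correcting before the final analysis, but it does not threaten the trial's main conclusions.

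**What to change.** - Replace the follow-up sentence in SAP section 7.1 so that double-blind by-visit tables and figures end at Week 8. Align Appendix A, in particular Table 2.1.3.5 and the ITT by-visit figures.
- Add one descriptive summary of within-subject change in EASI and IGA from EOT to follow-up, with loss of response among EOT responders, by route and last treatment received: (a) EOT at Week 8, by double-blind arm, noting that the triamcinolone arm's last treatment was vehicle; (b) EOT at Week 12 after open-label 1.5% BID; (c) early termination, as a listing only. Change measured from EOT also avoids the unequal baselines in SAP Table 1.
- State that the summary is non-randomized and that no between-arm durability comparison is made.

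The cost is SAP wording and one extra table from data already scheduled for collection. The drawback is that block (a) may have few subjects per arm.
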